The European CF community is close knit and meets and communicates regularly in order to develop a consensus on best practice. As such, management of CF in most EU countries is broadly uniform, with shared long term goals. This situation means that it is possible to undertake a registry study in a member state of the EU and extrapolate the results more broadly to the EU CF community. If significant differences in prescribing patterns are subsequently identified, the matching of patients by concomitant medication use should, in time, allow examination of specific sub-groups based on particular prescribing patterns that may be more favoured in a region.

The Cystic Fibrosis Trust in the UK currently has a well established and comprehensive patient registry. The UK CF Trust Registry represents one of the largest and most mature databases available in Europe and is broadly viewed as representative for the wider EU. Over 90 CF treatment centres in the UK contribute data to the registry and information is collected on more than 7,000 patients with CF annually.

The purpose of this study is to assess the rates of identified and potential risks of Bronchitol in CF through a comparison of Bronchitol-treated vs. non-treated patients in a matched cohort study from the CF registry over 5 year period. Safety analysis will be conducted and reported on a 6 monthly basis for the initial three year period and then annually for two years.

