# 6. RESEARCH METHODS

#### Study Population and Main Criteria for Inclusion:

Adult ( $\geq$  18 years) patients in the CF registry database who are prescribed Bronchitol. The unexposed group are untreated patients. These will be matched with treated patients on key characteristics.

At the time of the study starting, Bronchitol is only indicated for adult CF patients. Nevertheless, it may emerge that there are a significant number of paediatric and adolescent (6-17 years) patients who are prescribed Bronchitol "off-label". Furthermore, in time, an indication in children is also planned. If sufficient patient numbers make it feasible, a matched cohort of non-treated patients will be identified based on similar age, disease severity and concomitant medications (rhDNase, inhaled antibiotics, chronic antibiotics, presence of chronic Pseudomonas).

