#### 10. DATA ANALYSIS

This is a safety observational study, and therefore the focus is the safety endpoints (AEs of special interest).

At each analysis time a propensity score analysis will be performed. Here we will use logistic regression to estimate the probability of being treated with Bronchitol. This will generate a propensity score for each patient which will be used in subsequent analyses.

Full Analysis Population

All patients (treated and untreated) from CF Registry will be included in the analyses. For this population, we will include:

- Simple descriptive analyses (frequency and percentage) for AEs

- Negative Binomial regression for the count of events for each AE with adjustment for propensity scores.
- Cox regression for time to first event for each AE (Hazard Ratio), with adjustment for propensity scores.
- Matched Analysis Population

Analysis for the treated and matched untreated population will include:

- Descriptive analysis of the distribution of risk factors between the two groups of patients
- Simple descriptive analyses of AEs
- Negative Binomial regression for the count of events for each AE with and without any adjustment for potential confounders
- Negative Binomial regression assessing the interaction test between treatment and each important risk factor. Each risk factor will be tested one by one
- Subgroup analyses
  - Simple descriptive analyses and negative binomial regression (without any adjustment) for each AE for each subgroup. Subgroups will be defined a priori. Forest plots will be used to plot the Rate Ratios for all subgroups.

Cox regression will be used to study the time to first event for each AE. As for the negative binomial regression models these will be done both with and without adjustment for potential confounders.

Random effects linear models will be used to study changes in  $FEV_1$  over time. As with other regression models these will be performed with and without adjustment for potential confounders.

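### The subgroup rate ratios are fixed as unadjusted, and nothing in the protocol secures balance inside subgroups, so the forest plots can show confounding as effect modification

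*Protocol*

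**What the plan says.** Section 10 (Data analysis), under the matched analysis population, sets the subgroup analysis as "Simple descriptive analyses and negative binomial regression (without any adjustment) for each AE for each subgroup". It continues: "Forest plots will be used to plot the Rate Ratios for all subgroups". Subgroups are to be defined in advance, but the protocol does not list them.

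The overall comparison in the same population is treated differently: "Negative Binomial regression for the count of events for each AE with and without any adjustment for potential confounders". The Cox models and the random effects models for FEV1 follow the same two-way rule. The synopsis (Section 3) states that rule for modelling in general and makes no exception for subgroups.

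Effect modification is also tested formally: "Negative Binomial regression assessing the interaction test between treatment and each important risk factor". On this, Section 10 adds "Each risk factor will be tested one by one". It does not say whether these interaction models carry other covariates.

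On the unexposed patients, Section 6 says "These will be matched with treated patients on key characteristics". On the propensity score, Section 10 says "Here we will use logistic regression to estimate the probability of being treated with Bronchitol". The score is assigned explicitly as an adjustment in the full-population models. Its use for matching is neither stated nor excluded.

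**The concern.** This is a non-randomised comparison. Section 16 itself expects early use to be concentrated in sicker patients and relies on matching and propensity scores to control this. The subgroup models contain no propensity score and no covariates, so they rest on the matching alone.

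Matching balances the two groups over the whole cohort. When that cohort is split by a factor on which pairs were not exactly matched, treated patients and their controls can fall into different subgroups. A positive imbalance in one subgroup can then cancel a negative one in another, and the overall comparison of risk factors still looks clean. The only description of risk factors that Section 10 plans is between the two overall groups, so it would not reveal this.

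At stake is how a set of safety forest plots is read in reports that go to regulators (Section 13). A subgroup could appear to carry a raised risk, or a reassuringly low one, because of who was prescribed the drug.

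**Working it through.** The protocol gives no sample size, power, event rate or matching ratio, so it has no figure to reproduce. The check has two parts.

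**1. The text.** Within the matched population, adjustment is set as follows:

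- overall negative binomial, Cox and FEV1 models: unadjusted and adjusted;
- interaction models: not stated;
- subgroup negative binomial models: expressly unadjusted.

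No section says that matching is exact on the subgroup variables, repeated within subgroups, or checked for balance there. The lack of adjustment is therefore a stated rule and not a detail left open, and no other stated feature makes up for it.

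**2. The mechanism, by simulation.** All inputs are assumptions except N, which takes the registry size of more than 7,000 (Sections 4 and 8) as 7,000.

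- Subgroup S: binary, 50% prevalence. Confounder X (severity): standard normal.
- Treatment: logit P = −3 + 0.3·S + 0.5·X + 2·d·(S − 0.5)·X. The slope on X is 0.5 − d when S = 0 and 0.5 + d when S = 1.
- Event counts: negative binomial, dispersion 1, log mean = −1 + 0.2·S + 0.5·X. There is no treatment term, so the true rate ratio is 1.00 in both subgroups.
- Matching: 1:1 nearest neighbour on a propensity score with main effects of S and X, caliper 0.2 SD of the logit, giving about 430 to 480 pairs.
- 60 replicates per row. Paired entries are S = 0, then S = 1.

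| d | Slopes on X | Exact match on S | X difference overall (SD) | X difference by subgroup (SD) | Overall RR | Unadjusted RR by subgroup | Adjusted RR by subgroup |
|---|---|---|---|---|---|---|---|
| 0 | 0.50, 0.50 | no | 0.00 | −0.01, +0.01 | 0.99 | 1.01, 0.99 | 1.02, 0.98 |
| 0 | 0.50, 0.50 | yes | 0.00 | 0.00, 0.00 | 0.99 | 1.02, 0.98 | 1.03, 0.98 |
| 0.25 | 0.25, 0.75 | no | −0.01 | −0.21, +0.12 | 0.96 | 0.86, 1.01 | 0.98, 0.97 |
| 0.25 | 0.25, 0.75 | yes | 0.00 | 0.00, 0.00 | 0.98 | 1.00, 0.97 | 1.00, 0.97 |
| 0.5 | 0.00, 1.00 | no | −0.02 | −0.35, +0.15 | 1.00 | 0.77, 1.09 | 0.98, 1.03 |
| 0.5 | 0.00, 1.00 | yes | 0.00 | 0.00, 0.00 | 1.02 | 0.98, 1.04 | 0.99, 1.03 |

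The rows without bias scatter between 0.97 and 1.04, so departures of a few hundredths should be read as simulation noise.

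The false contrast between subgroups, without exact matching, is the ratio of the two subgroup rate ratios:

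- d = 0.5: 1.09 / 0.77 = 1.42 unadjusted, against 1.03 / 0.98 = 1.05 adjusted.
- d = 0.25: 1.01 / 0.86 = 1.17 unadjusted, against 0.97 / 0.98 = 0.99 adjusted.

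The direction agrees with a first-order calculation from the mean imbalance. For d = 0.5, exp(0.5 × −0.35) = 0.84 and exp(0.5 × 0.15) = 1.08. This is only approximate, because mean counts depend on the whole distribution of X and not just its mean.

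A separate simulation used other assumptions: 4,000 patients, 200 cohorts, slopes on severity of 0.3 and 0.3 + 0.7 = 1.0, dispersion 0.5. It gave 1.00 overall, 0.84 and 1.05 in the unadjusted subgroups, and 1.00 and 1.01 after adjustment.

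**The case against.** The strongest reply is that the subgroup models are fitted in matched data. Leaving covariates out of the regression does not undo the matching. A reader might infer that these rate ratios have no protection against confounding by indication, or that false signals must follow from the rule. The documents do not support that. Matching gives partial protection, and the simulation shows no bias when severity drives prescribing equally in both subgroups, or when pairs are exactly matched on the subgroup variable. The protocol may turn out to meet either condition; it secures neither.

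The matching method in the simulation is also an assumption. The protocol speaks of matching on key characteristics and does not say that this is done on the propensity score. Nothing in it indicates how strongly prescribing varies with severity across subgroups. This objection stands against any claim about size.

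Two further inferences go too far. One is that the subgroup models are the only ones in the matched population not run both ways: the interaction models leave their adjustment unstated. Those tests are a partial safeguard, but they do not correct the plotted rate ratios. The other is that carrying the results to the rest of the EU depends on these subgroups. Section 4 rests that extrapolation on broadly uniform CF management and treats regional subgroups as a contingency, where "the matching of patients by concomitant medication use should, in time, allow examination of specific sub-groups". Those particular subgroups would be defined on a stated matching factor and may be better balanced than others, although exactness is not stated.

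Finally, the subgroup results are supportive in a study aimed at estimation (Section 9), and the primary comparison is not affected.

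**Conclusion.** The point holds as a conditional weakness that is cheap to remove. The protocol expressly rules out adjustment in the subgroup models, gives no reason, and departs from the practice it sets for the overall matched models. Because balance inside subgroups is not secured, the forest plots can present confounding as a difference in treatment effect.

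Under the assumptions shown, with a true rate ratio of 1.00, unadjusted subgroup values ran from no bias to about 0.77 and 1.09, and adjusted values lay between 0.97 and 1.03. The recovery is a best case, since the simulated model adjusted for the one confounder that existed; in practice only measured confounders can be handled. The actual size in this registry cannot be derived from the documents. The overall matched analysis is not called into question.

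**What to change.** In Section 10, delete the parenthesis that rules out adjustment and apply to each subgroup the same pair of analyses as for the main matched models, unadjusted and adjusted for potential confounders. Plot the adjusted rate ratios, with the unadjusted ones alongside. Extend the planned description of risk factors so that covariate balance is shown within each subgroup.

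The defect does not require a single joint interaction model or variance clustered on matched sets; those are separate choices.

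The cost is a change of wording and some extra output. The protocol does not name its confounders, but the main adjusted models need that list anyway. The downside is that adjusted models may fail to converge in very small subgroups; there, counts and percentages can be reported without a model.

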# **11. PROTECTION OF HUMAN SUBJECTS:**

In order to safeguard the well-being and rights of participants in this post-authorisation safety study, the CF Trust will comply with all relevant laws of the European Union that are directly applicable or of direct effect and all relevant laws and statutes of the UK country in which the CF Trust Patient Registry is located. These include, but are not limited to, the Human Rights Act 1998, the Data Protection Act 1998, the Medicines Act 1968, the Medicines for Human Use (Clinical Trial) Regulations 2004, and with all relevant guidance relating to medicines and clinical trials from time to time in force including, but not limited to, the ICH GCP, the World Medical Association Declaration of Helsinki entitled 'Ethical Principles for Medical Research Involving Human Subjects' (1996 version), the NHS Research Governance Framework for Health and Social Care (version 2, April 2005).

#### 12. MANAGEMENT AND REPORTING OF ADVERSE EVENTS/ADVERSE REACTIONS

Adverse events will not be reported on an expedited basis for this study as it is an observational cohort study designed to collect long-term safety information using secondary data. All safety information will be assessed and submitted in interim analysis reports and will be submitted according to the schedule agreed as part of the post-authorisation commitment for this study. A full review of the safety information collected for the full study period will be presented in the final study report.

# 13. PLANS FOR DISSEMINATING AND COMMUNICATING STUDY RESULTS

Interim analysis will be performed 6 monthly for 3 years and then annually for 2 years, the final study report is expected in Q4 2017. Interim and final safety reports from this study will be submitted to appropriate regulatory agencies.

Policies regarding the publication and presentation of study data are defined in the Service Agreement between Pharmaxis Ltd and Cystic Fibrosis Services Limited.

#### **14. QUALITY ASSURANCE**

The UK CF Registry has regular quality testing by the hosting company with respect to the encryption and safety of the data held. The application is held in Amsterdam in accordance with EU recommendations. There are elaborate encryption protocols in the production of user access including a unique person specific username and unique password. The password has to be changed every 30 days. The data can only be seen by the user site and data cannot be moved between sites without the Registry team being involved. The registry is in the process of receiving the SLSP (Short Leap Shared Protection) Certificate and has the Secure Site Pro SSL Certificate required for large databases.

Within the Registry there are inbuilt verification tools which will "flag up" any abnormal values which are out with normal ranges directly to the sites and in some instances to the Registry Team. Throughout the year regular (monthly) data verification is carried out by the Registry Team running programmes looking at unusual data entries eg: abnormal Height, Weight etc. Any queries are then reported back to the sites for verification. Any duplicate registration of patients is also checked on a monthly basis and if found records merged with no loss of data. Thus maintaining a "clean" data set of patients.

Before any data cut is requested from the Hosting Company extensive data cleaning is undertaken in conjunction with the Bio-Statisticians at Imperial College London.

The Registry is run from the Cystic Fibrosis Trust in a password protected, locked office in accordance with the Ethical requirements for approval of the Registry. The Registry Team are "trusted third parties" and conform to the Data Protection Act in full.

Centres and Clinics will be monitored on a regular basis by the Registry Team. Study monitoring visits will be scheduled with the sites on a regular basis to ensure data is recorded in the patient notes as well as on the registry and in accordance with usual practice. All entries will be checked to ensure entries are correct. If there are any discrepancies then these will be documented and then verified with the sites. The logs for these visits will be kept up to date. Random sets of patients' notes will be checked at the visits so ensuring no bias.

In addition the regular monthly data verification will be continued by the Registry Team. There is a Registry Helpdesk which answers queries within 24 hours and all sites will be encouraged to use this for any queries. In addition the Registry Team will be contactable via email and telephone.

# **15. FINANCING AND INSURANCE**

A financial agreement will be made between Pharmaxis Ltd and the UK CF Trust prior to commencement of the study.

The study is covered under the CF Trust liability insurance policy. The certificate of insurance and essential information about the policy can be provided upon request from the CF Trust.

# 16. GENERALISABILITY, LIMITATIONS AND POSSIBLE BIAS

The clinical use of a newly licensed product may often be predominantly limited to a more severe patient population in the first 6-12 months. The initial subjects studied may therefore not be representative of the whole CF population; however the matching cohort strategy will limit this potential bias. Additionally, the analytical models being employed include propensity scores thus controlling for the probability of being prescribed Bronchitol.

In addition, the majority of CF centres in the UK contribute data, so the CF Registry is able to be generalised to the UK CF population. As the UK CF Registry is one of the largest and most mature databases available in Europe, it can be viewed broadly as representative for the wider EU. If however, significant differences in prescribing patterns are identified, the matching of patients should, in time, allow examination of specific sub-groups based on particular prescribing patterns that may be more favoured in a region.

A limitation of having an adult's only label is that the data analysis will only be for the adult population. As it is not possible to predict any off-label usage in children and adolescents and also usage is likely to be very small, this data will only be provided in summary format.

A limitation in using routinely collected registry data in epidemiological research is that for some outcomes, such as the acquisition of new microbial infections and increased use of oral steroids, we do not have a precise date on which the outcome occurred. As such, the date of the event will be estimated based on when the annual review encounter took place. In the first annual review after

the index date, it is therefore possible that either of these two outcomes are mis-identified as being post-index date when the event may have occurred prior.

All analysis and reporting will be done independently by Imperial College for the Cystic Fibrosis Trust and in liaison with the Lead Investigator. Pharmaxis will receive the analyses at the different time points and include them as required in reports to the international regulatory bodies.

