#### 5. RESEARCH QUESTIONS AND OBJECTIVES

Primary Objective:

To assess the rates of identified and potential risk of Bronchitol in CF through a comparison of Bronchitol treated vs. non-treated patients in a cohort matched for key characteristics from the CF registry over a 1 to 5 year period. Safety analysis would be conducted on a 6 monthly basis for three years and then annually for two further years.

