#### 7. STUDY DESIGN

This is an observational cohort study which aims to collect anonymised data on all subjects taking Bronchitol who contribute annual data to the UK CF Registry and matched, untreated subjects. Data from individual subjects is currently entered into the Registry database annually. Data on treated and untreated patients will be analysed on a regular basis (at six-month intervals for the initial three years and then annually).

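### For outcomes dated only at the annual review, events from before Bronchitol can be counted as post-index, and the protocol states no analysis to separate them

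*Protocol*

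**What the plan says.** Section 16 of the protocol gives examples of outcomes whose timing is not recorded: "such as the acquisition of new microbial infections and increased use of oral steroids, we do not have a precise date on which the outcome". It then fixes a rule: "the date of the event will be estimated based on when the annual review encounter took place". It draws the consequence itself for the first post-index review, namely that "it is therefore possible that either of these two outcomes are mis-identified as being post-index date when the event may have occurred prior". The paragraph ends there. No exclusion, lag, event-free restriction or sensitivity analysis follows.

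Section 7 gives the data rhythm: "Data from individual subjects is currently entered into the Registry database annually". Analyses are more frequent: "at six-month intervals for the initial three years and then annually".

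Section 10 plans negative binomial models for the count of each adverse event and, for the matched population, "Cox regression will be used to study the time to first event for each AE". It makes no exception for outcomes without a date.

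The index date is mentioned only in Section 16. It is not defined there for treated or untreated patients.

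**The concern.** The first review after a patient starts Bronchitol looks back over an interval that straddles the start. An infection or steroid increase found there may belong to either side, and the dating rule places all of it after the start.

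Matching and propensity scores, which Section 16 relies on against selective prescribing, balance patient characteristics. They do not move a misdated event. Section 16 also expects that "The clinical use of a newly licensed product may often be predominantly limited to a more severe patient population" in the first 6-12 months, so unequal event rates before the index date are plausible.

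Two errors are possible in a safety study whose interim reports go to regulators: a real harm is diluted, or events that preceded treatment appear as a harm of it. With data entered yearly and reports every six months, the exposure is greatest early. If reviews are about 12 months apart and treatment starts on or after 01/07/2012, almost any post-index review up to 30/06/2013 is a first post-index review. For these outcomes, the first two data periods in Section 17 would then rest almost wholly on the mixed interval.

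**Working it through.** The protocol gives no event rate, misclassification rate or sample size for this point, so there is no stated figure to reproduce. The calculation is illustrative.

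**Inputs from the protocol.** Annual data entry (Section 7); events dated at the review (Section 16); follow-up "in a cohort matched for key characteristics from the CF registry over a 1 to 5 year period" (Section 5).

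**Assumptions, not in the protocol.** Reviews are 12 months apart. Treatment starts a fraction *u* of the way through the gap between reviews (0.5; range 0.25 to 0.75). Rates are constant, and the control rate is set to 1 per year. Matched controls have the same *u* unless stated. *R* is the true rate ratio after index, *m* is the treated-to-control rate ratio before index, and *k* is the number of post-index reviews.

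**Share of counted events that are pre-index**, when rates before and after index are equal: *u/k*.
- First review: 0.5/1 = 50% (25% to 75%).
- Through two reviews: 0.5/2 = 25%.
- Through five: 0.5/5 = 10% (5% to 15%).

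**Observed rate ratio.** Treated events counted are *u·m + (k − u)·R*; control events are *u + (k − u) = k*. Both groups have person-time *k − u*, which cancels:

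observed ratio = [*u·m + (k − u)·R*] / *k*

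With *u* = 0.5:

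| Case | k = 1 | k = 2 | k = 5 |
|---|---|---|---|
| R = 1, m = 1 | (0.5 + 0.5)/1 = 1.00 | (0.5 + 1.5)/2 = 1.00 | (0.5 + 4.5)/5 = 1.00 |
| R = 2, m = 1 | (0.5 + 1)/1 = 1.50 | (0.5 + 3)/2 = 1.75 | (0.5 + 9)/5 = 1.90 |
| R = 1.5, m = 1 | (0.5 + 0.75)/1 = 1.25 | (0.5 + 2.25)/2 = 1.375 | (0.5 + 6.75)/5 = 1.45 |
| R = 1, m = 1.5 | (0.75 + 0.5)/1 = 1.25 | (0.75 + 1.5)/2 = 1.125 | (0.75 + 4.5)/5 = 1.05 |
| R = 1, m = 2 | (1 + 0.5)/1 = 1.50 | (1 + 1.5)/2 = 1.25 | (1 + 4.5)/5 = 1.10 |

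Over *u* = 0.25 to 0.75, the first-review figure for R = 2, m = 1 runs from 1.75 down to 1.25. For R = 1, m = 1.5 it runs from 1.125 to 1.375.

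**Index dates not aligned.** Suppose a control's index date is set at a review, so that none of the look-back is pre-index. With R = 1 and m = 1 the observed ratio is *k/(k − u)*: 1/0.5 = 2.0 at the first review (1.33 to 4.0) and 5/4.5 = 1.11 through five. The false signal here comes from the index rule alone.

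**Cox model, by simulation.** 20,000 patients per group, control rate 0.15 per year, *u* uniform on 0 to 1, first events dated to the review. The last column starts follow-up at the first post-index review in patients event-free there.

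| True HR | Pre-index ratio | One review | Five reviews | Five reviews, lagged start |
|---|---|---|---|---|
| 1 | 1 | 0.98 | 1.01 | 1.01 |
| 1 | 1.5 | 1.24 | 1.08 | 1.00 |
| 1 | 2 | 1.41 | 1.13 | 0.99 |
| 1.5 | 1 | 1.21 | 1.43 | 1.48 |
| 2 | 1 | 1.48 | 1.84 | 1.87 |

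The lagged start removes the false signal. The shortfall left in the last two rows is attributed to the heavy ties created by annual dating; it is small.

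**The case against.** The protocol discloses the problem. It names the data constraint, two affected outcomes and the review at which the error arises. At-risk windows, lags, tie handling and sensitivity analyses are commonly left to a statistical analysis plan, which is not shown here. That would dispose of the point if the protocol were silent, but it sets the dating rule itself. Its warning also makes sense only if the first post-index review is counted. That the review is kept is therefore an inference, but a sound one.

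Scope is also inferred. Section 10 does not list these two outcomes among the events modelled, and the study-size section names only haemoptysis and bronchospasm, for which no dating problem is stated. This stands as a limit on reach: the point concerns undated outcomes, not the whole safety comparison.

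A reader might infer more: that pre-treatment events will certainly be counted as harms, that they are what prompts the prescription, and that the comparison is wrong in every case. The documents do not support this. Section 16 says only that misidentification is possible. It describes use in more severe patients, not prescribing triggered by an infection or a steroid increase. The pre-index ratios used above have no source in the protocol.

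Finally, delaying the start of follow-up has a real price. The first countable event then appears at the second post-index review, 12 to 24 months after starting (about 18 on average if starts are spread evenly between reviews). Early on-treatment events are lost, and the analysis is restricted to patients who stayed event-free after exposure. This argues against replacing the current definition, but not against reporting a lagged analysis beside it.

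**Conclusion.** The point holds, at moderate severity. The protocol fixes a dating rule that can place pre-index events after the index date, says so, and states no analysis that would show how much of a result comes from them.

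The direction depends on conditions the protocol leaves open: dilution of a true effect when pre-index rates are equal, a false signal when treated patients had more events before starting or when index dates differ in kind between the groups, and no bias when none of these applies. The distortion matters most in early reports and largely fades. At a pre-index ratio of 1.5 and no true effect, the rate ratio is 1.25 at the first review and 1.05 through five (simulated Cox: 1.24 and 1.08). These sizes rest on 12-month gaps, mid-gap starts, constant rates and assumed pre-index ratios. Ties in the Cox model are a secondary matter.

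**What to change.** - Define the index date for both groups, giving each matched control the index date of its treated partner.
- For new microbial infection and increased oral steroid use, count only outcomes absent at the last pre-index review. This removes conditions already present, but not events between that review and the index date, so the next step is still needed.
- Pre-specify, and show beside the current definition in every report, a lagged analysis: follow-up starts at the first post-index review, in patients event-free at that review, under the same rule for controls. Use a discrete-time model (complementary log-log link) by annual interval.
- State the reading rule: a signal under the current definition is taken as post-treatment only if it persists in the lagged analysis or is otherwise explained as an early effect.

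The cost is some wording and a little programming. The lagged analysis gives up about six months of post-index time per patient on average, misses early on-treatment events and has little data in the first reports. That is why the current definition stays beside it.
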